13.5 Future Use of Stored Specimens

We will request participation in storage of blood samples collected for continued analyses of this study, for studies as new scientific discoveries are made, to allow for retesting if necessary and for future research related to cardiovascular risk. We will give subjects who participate in the study the option to opt into storage for future research as there are many unknowns about cardiovascular risk in patients with air pollution exposure, and being able to maintain the samples will allow us to build upon the knowledge we gain from this initial study. Patients will be informed of this during the consent process. Future research will not stray from the purpose of the original application, and optional participation in the storage of samples for future research will remain separated from the primary protocol. For optional future research, we will collect an additional \approx 10 mL of blood at both the baseline and final blood draws.

Blood samples for future analysis will be assigned a unique code number and stored in a dedicated freezer storage by the PI without any identifying information other than a code number. The unique code number will not be based on any information that could be used to identify the subject (for example, social security number, initials, or birth date). We will use freezer-safe labels and store samples in freezers with emergency backup power. The master list linking names to code numbers will be kept in a locked file cabinet, separate from all research information, under double lock and key. Only the NYU PI will have access to the linking key between subject ID and subject identity. All confidential data will be stored with a unique code as an identifier and will be protected by a double electronic lock. All physical data will be kept under double physical lock. Only the PI and Co-Is will have access to the banked samples.

Samples will be stored for no more than 20 years. The specimens for future analysis may be analyzed upon completion of the study for RNA, microRNA, and DNA. The blood specimens may be analyzed upon completion of the study for RNA, microRNA, and DNA profiling. This may include detailed molecular profile study, describing genetic arrays of patterns associated with cardiometabolic risk. We will not be performing whole genome sequencing, only genetic testing as it relates to cardiovascular risk described above. Because there is no potential for clinically actionable genetic incidental findings because of this testing, genetic information will not be disclosed to anyone, including the participants and their physicians. Samples could also be used for testing other potential biomarkers in patient plasma and/or serum related to diabetes and CVD that may occur with exception of those which are already part of the protocol. Results of the future research will not be shared with the subjects or their physician, and will not become part of the participants' medical records.

In the future, other institutions, or future collaborators at or outside of NYU Medical Center may want to study a portion of these samples. If that happens, samples would be sent to other places so other people interested in studying these diseases and conditions could do that. The samples sent to other researchers will be de-identified without PHI. Samples will be stored for no more than 20 years following completion of the study. At the end of the 20-year period, all samples will be destroyed.

Subjects can request for withdrawal of samples at any time by contacting PI [name] in writing. His mailing address is NYU Translational Research Building, [name]. Withdrawing Authorization only affects uses and sharing of information after written request has been received, and subject may not withdraw his/her Authorization for uses or disclosures that have previously been made or must continue to complete analyses or report data from the research.

14 Data Handling and Record Keeping

14.1 Data Collection and Management Responsibilities

Data collection is the responsibility of the study staff at the site under the supervision of the site PIs. The investigator is responsible for ensuring the accuracy, completeness, legibility, and timeliness of the data reported.

All source documents should be completed in a neat, legible manner to ensure accurate interpretation of data. Black ink is required to ensure clarity of reproduced copies. When making changes or corrections, cross out the original entry with a single line, and initial and date the change. DO NOT ERASE, OVERWRITE, OR USE CORRECTION FLUID OR TAPE ON THE ORIGINAL.

Copies of the electronic CRF (eCRF) will be provided for use as source documents and maintained for recording data for each participant enrolled in the study. Data reported in the eCRF derived from source documents should be consistent with the source documents or the discrepancies should be explained and captured in a progress note and maintained in the participant's official electronic study record.

Clinical data (including AEs, concomitant medications, and expected adverse reactions data) and clinical laboratory data will be entered into RedCAP. The data system includes password protection and internal quality checks, such as automatic range checks, to identify data that appear inconsistent, incomplete, or inaccurate. Clinical data will be entered directly from the source documents.

For questionnaires confirming inclusion/exclusion criteria, data will be entered on an iPad with a data plan, provided by NYUMC, and stored using REDCap. No identifiable information will be entered or will be able to be accessed by field staff. In addition, iPads will be programmed to limit access to only REDCap prior to data collection. Back-up paper forms will be used in the event of technology issues. After data cleaning and quality assurance procedures are completed, pertinent sets of data will be converted into SAS format for statistical analyses. Only authorized research staff will have access to the files.

14.2 Study Records Retention

Study documents will be retained for at least 5 years after final reporting/publication. No records will be destroyed without the written consent of the sponsor.

14.3 Protocol Deviations

All deviations in protocol will be addressed in study source documents, reported to the NYULMC IRB.

14.4 Publication and Data Sharing Policy

This study will comply with the NIH Public Access Policy, which ensures that the public has access to the published results of NIH funded research. It requires scientists to submit final peer-reviewed journal manuscripts that arise from NIH funds to the digital archive PubMed Central upon acceptance for publication.

The International Committee of Medical Journal Editors (ICMJE) member journals have adopted a clinical trials registration policy as a condition for publication. The ICMJE defines a clinical trial as any research project that prospectively assigns human subjects to intervention or concurrent comparison or control groups to study the cause-and-effect relationship between a medical intervention and a health outcome. Medical interventions include drugs, surgical procedures, devices, behavioral treatments, process-of-care changes, and the like. Health outcomes include any biomedical or health-related measures obtained in patients or participants, including pharmacokinetic measures and adverse events. The ICMJE policy, and the Section 801 of the Food and Drug Administration Amendments Act of 2007, requires that all clinical trials be registered in a public trials registry such as ClinicalTrials.gov, which is sponsored by the National Library of Medicine. Other biomedical journals are considering adopting similar policies. For interventional clinical trials performed under NIH IC grants and cooperative agreements, it is the grantee's responsibility to register the trial in an acceptable registry, so the research results may be considered for publication in ICMJE member journals. The ICMJE does not review specific studies to determine whether registration is necessary; instead, the committee recommends that researchers who have questions about the need to register err on the side of registration or consult the editorial office of the journal in which they wish to publish.

FDAAA mandates that a "responsible party" (i.e., the sponsor or designated principal investigator) register and report results of certain "applicable clinical trials":

- Trials of Drugs and Biologics: Controlled, clinical investigations, other than Phase I investigations of a product subject to FDA regulation;
- Trials of Devices: Controlled trials with health outcomes of a product subject to FDA regulation (other than small feasibility studies) and pediatric postmarket surveillance studies.
- NIH grantees must take specific steps to ensure compliance with NIH implementation of FDAAA.

15 Study Finances

15.1 Funding Source

This study is financed through a pilot grant from the NYU CTSI under grant number NIH/NCATS UL1TR001445

15.2 Costs to the Participant

No costs will incur as a result of participating in the study.

15.3 Participant Reimbursements or Payments

Individual participants will be remunerated for blood draws as follows: Participants will receive \$25 after the baseline blood draw. Upon completing the study, participants will be allowed to keep the air cleaner,

and will be given a true filter if assigned to the “sham” group; participants will also keep the blood pressure cuff. Participants will receive \$75 after all other equipment is returned (electricity monitor, air pollution monitor and blood pressure data hub) and the final blood draw is completed.

16 Study Administration

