5.7 Participant Withdrawal or Termination

5.7.1 Reasons for Withdrawal or Termination

This is a minimal risk study, so we do not expect participants to withdraw for a safety related issue. However, participants are free to withdraw from participation in the study at any time upon request. If patients need to sleep elsewhere than their own bedroom for any unanticipated reason during the trial,

they should notify the research team and study endpoints (exposures and SBP) will be excluded from analyses during this period. Participants that unexpectedly require sleeping 2 or more consecutive nights away from their home (or a total of 7 days altogether) during the study period will need to drop from the study and their data will not be used in analyses. They can re-enroll at a later date.

Reasons for withdrawal may be moving from the area or simply not interested in participating further.

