5.7.2 Handling of Participant Withdrawals or Termination

Participation is voluntary and all study participants may withdraw from the study at any time without penalization. Participants may request removal and destruction of their blood samples from storage for future research without withdrawal from the remainder of the study. Participants may request termination from the study separate from withdrawal from future research.

No replacement of participants who withdraw or discontinue early will occur. Data including date and reason for withdrawal will be recorded.

A participant is considered lost to follow-up after 10 attempts to contact them by phone and 10 attempts by Epic messaging.

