6.1 Study Agent(s) and Control Description

This study will utilize a sham PAC as a control. PAC will be delivered to participants as active or sham PAC in blinded fashion. The study team will receive the new devices and remove filters from sham PACs. Filters will be stored in our research office until the participant completes the protocol, at which time participants will return study equipment at receive filters to keep. Filter status indicator lights on the PAC will be covered with black electrical tape on all devices (active and sham) to preserve blinding.

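### Data are excluded for nights away, but no form shown asks about them and, at the drop threshold, disclosure puts the $75 final payment at risk

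*Combined protocol and SAP*

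**What the plan says.** Section 5.7.1 has two tiers. For an unanticipated need to sleep elsewhere, it tells participants that "they should notify the research team and study endpoints (exposures and SBP) will be excluded from analyses during this period". The upper tier begins "Participants that unexpectedly require sleeping 2 or more consecutive nights away from their home (or a total of 7 days altogether" and says that these participants "will need to drop from the study and their data will not be used in analyses". It then adds "They can re-enroll at a later date".

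Section 15.3 pays $25 after the baseline draw and $75 "after all other equipment is returned (electricity monitor, air pollution monitor and blood pressure data hub) and the final blood draw is completed". On the device it says "Upon completing the study, participants will be allowed to keep the air cleaner", with a true filter for the sham group. Section 2.3.2 lists keeping the air cleaner as a benefit with no completion condition, and the return list for the withdrawal visit (Section 7.7) leaves it out. Section 6.1 says "Filters will be stored in our research office until the participant completes the protocol". Section 5.7.2 says that participants "may withdraw from the study at any time without penalization".

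The Aim 2 exposure (Section 10.3) is the change from baseline to a time-weighted average of bedroom PM2.5. Section 10.2 declares an intention-to-treat dataset.

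**The concern.** A rule that removes data needs a source that says when it applies. Here that source is a participant who speaks up unprompted, and at the drop threshold speaking up may cost that participant most of the study payment. Two people with the same absence can then be handled differently: one loses data or is dropped, while the other stays in with PM2.5 recorded in a room that nobody slept in. What is at stake is mainly the individual exposure value in Aim 2, and through it the PM2.5 term in Exploratory Aim 2. The Aim 1 comparison of arms is much less exposed.

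**Working it through.** The plan gives no figure on this point to reproduce. The check is a reading of the documents followed by simple arithmetic.

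**1. Does anything ask?**
- The final visit list (Section 7.6) covers equipment return, blood collection and a timing limit.
- The Post-Intervention Questionnaire (Attachment A) asks how long the filter ran each day and whether blood pressure medication changed. It does not ask where the participant slept.
- The blood pressure log (Attachment B) and the setup sheet (Attachment C) do not ask.
- Inclusion criterion 8 (Section 5.1) records intention at entry only.

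**2. Could a monitor stand in?**
- The electricity monitor shows that the device is running. The PM monitor records whether or not anyone is in the room.
- Gaps in blood pressure readings are not specific. Section 4.1 anticipates up to 30% missing. Take 30% of 28 mornings missing independently (assumption, top of the stated range) in someone who never left home.
- Run of 2 or more missing mornings: let a and b be the probabilities of no such run so far with the last morning present or missing. Start at a = 1, b = 0 and update a' = 0.7(a + b), b' = 0.3a. After 28 steps, 1 − a − b = 0.874, or 87%.
- Seven or more missing mornings: P(X ≥ 7) for X ~ Binomial(28, 0.3) = 0.780, or 78%.
- Missing readings therefore cannot identify absence.

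**3. What does disclosure cost?**
- Below the threshold: that period's data are removed, and nothing in Section 15.3 changes.
- At the threshold: the participant is dropped. The withdrawal visit in Section 7.7 has no blood draw, so the condition for the second payment is not met. Share at risk: 75 / (25 + 75) = 75%.
- Re-enrolment is allowed, but no section says what a re-enrolled participant is paid.

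**4. How much of the PM2.5 average is affected?** Share = days / window for full days, and (days × 8) / (window × 24) if only 8 sleeping hours a day count (assumption). Section 10.3 names a 14-day window although the intervention lasts 4 weeks, so both windows are shown.

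| Undeclared days | 28-day, full days | 28-day, 8 h | 14-day, full days | 14-day, 8 h |
|---|---|---|---|---|
| 2 | 2/28 = 7.1% | 16/672 = 2.4% | 2/14 = 14.3% | 16/336 = 4.8% |
| 7 | 7/28 = 25.0% | 56/672 = 8.3% | 7/14 = 50.0% | 56/336 = 16.7% |

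**5. Arm level.** If 10% of participants hide 4 nights (assumption), the share of exposure time affected is 0.10 × 4/28 = 1.4%.

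**The case against.** Several stronger readings are tempting, and the documents do not support them.

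- *Any report of a night away costs the participant.* It does not. Section 5.7.1 is tiered, and the payment is at risk only at the drop threshold. Re-enrolment may turn the loss into a delay.
- *A dropped participant loses the air cleaner.* This can only be inferred from the completion wording in Section 15.3. Sections 2.3.2 and 7.7 point the other way, and no section requires the device to be returned. It is a contradiction to reconcile, not an established loss.
- *The payment rule breaks the promise in Section 5.7.2.* That section concerns voluntary withdrawal, and Section 15.3 pays for blood draws. Not paying for a draw that was not taken is a tension at most.
- *Sham participants who stop early are left uninformed with an unfiltered machine.* The stored filter is tied to completion, so the gap in the text is real. What participants are told cannot be checked, because the consent pages are not in the text reviewed.
- *Blood pressure taken elsewhere is counted as on treatment.* Attachment C has the data hub plugged in near where readings are taken at home. The documents do not say whether readings taken away would transmit.

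It is also fair to say that Section 11 mentions checklists and tracking sheets that are not reproduced and might ask about nights away. A room-level, round-the-clock average already includes hours when the participant is out. Finally, for Aim 1, keeping people who were away is what intention-to-treat requires, so asking everyone while leaving the drop rule as it stands would increase post-randomisation exclusions.

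These points limit the finding. They do not supply the missing data collection behind the plan's own exclusion rule. The last one shapes the remedy.

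**Conclusion.** The concern holds in a limited form. An exclusion rule depends on unprompted self-report, and at the 2-consecutive-night or 7-day threshold the payment schedule gives a reason not to report. Some PM2.5 from an unoccupied bedroom can therefore stay in the Aim 2 average. For an affected person with 2 to 7 undeclared days, the share is 7% to 25% of a 28-day average counting full days, or about 2% to 8% counting 8 sleeping hours; a 14-day window doubles these. A reader might infer that the treatment comparison is materially diluted, but the illustrative arm-level figure is only about 1.4%. The number of participants who would be away and not say so is unknown; the 10% and the 4 nights are assumptions. The absence of any prompt is established only for the visit lists and forms shown. This is a cheap improvement and not a threat to the Aim 1 result.

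**What to change.** 1. Add to the Post-Intervention Questionnaire, and list in Section 7.6, an item put to every participant that asks for the dates slept outside the study bedroom. Use those dates to remove the matching days from the PM2.5 average and home systolic pressure in Aim 2 and Exploratory Aim 2 only. Keep every randomised participant who has a final draw in the Aim 1 intention-to-treat analysis, and reconcile the data-removal sentence in Section 5.7.1 with Section 10.2.
2. State in Section 15.3, and tell participants, that payment does not depend on the answer.
3. Reconcile Sections 2.3.2, 6.1, 7.7 and 15.3 on what happens to the air cleaner and the stored filter when a participant stops early.

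Cost: one questionnaire item and protocol wording, plus up to $75 for each affected participant. At an assumed 10% of 44 this is 4.4 × $75 = $330. Sections 4.1 and 5.6 give 74 participants instead; at 10% of 74 it is 7.4 × $75 = $555. Removing dated days does not recover what the participant breathed elsewhere, but it lets the plan's own rule apply to everyone alike.

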Attachment A : Air Filter Pilot Study Questionnaire

Pre-Intervention Questionnaire:

Height and Weight Measurements (self-reported measures):

Enter the respondent's weight (lbs.) here. Weight to the nearest 0.2 lb.: XXX

Enter the respondent's height (inches) here. Height to the nearest 0.5 in.: XXX

1. How long have you had high blood pressure?
 - a. 0-2 years
 - b. 2-5 years
 - c. 5-10 years
 - d. >10 years
 - e. Don't know/refused
2. How long as it been since you last had your blood pressure taken by a doctor or other health professional? Was it...
 - a. Within the past month?
 - b. 1-6 months ago?
 - c. 6-12 months ago?
 - d. Over 1 year ago?
 - e. Don't know/refused
3. Have you ever been told to take prescription medicine because of high blood pressure?
 - a. Yes
 - b. No
 - c. Don't know/refused
4. Have you been told to take or continue taking prescription medicine because of high blood pressure/hypertension in the past 12 months?
 - a. Yes
 - b. No
 - c. Don't know/refused
5. *[If yes to Q3/Q4]:* Are you now taking prescription medicine?
 - a. Yes
 - b. No
 - c. Don't know/refused
6. Have you ever been told you have an inflammatory disorder such as rheumatoid arthritis, inflammatory bowel disease, cancer?
 - a. Yes
 - b. No
 - c. Don't know/refused
7. If you take medications to lower your blood pressure, have any of these medications changed in the last month?
 - a. Yes
 - b. No
 - c. Don't know/refused
8. In the past month, how often have you checked your blood pressure at home?
 - a. Never
 - b. Less than weekly
 - c. Weekly

- d. More than weekly
- 9. Have you ever had, or been told you had, a heart attack?
 - a. Yes
 - b. No
 - c. Don't know/refused
- 10. Have you ever had, or been told you had, a stroke?
 - a. Yes
 - b. No
 - c. Don't know/refused
- 11. How concerned are you about the effects of air pollution on your health?
 - a. Extremely concerned
 - b. Very concerned
 - c. Somewhat concerned
 - d. Mildly concerned
 - e. Not concerned

(On Day 0, trained field staff will enter participant's home, and place field equipment inside their home, providing detailed demonstration on how to measure blood pressure. Trained field staff will also manually record participant's height and weight (lbs.) using a digital scale)

Post-Intervention Questionnaire:

Now that you have an air filter, I have some questions for you:

- 1. How much time each day did you spend checking your BP for the study?
 - a. 2-5 minutes
 - b. 5-10 minutes
 - c. 10-15 minutes
- 2. On average, how much time did you run the filter each day?
 - a. I kept it on for 24 hours a day
 - b. I ran it for most of the day (18-24 hours)
 - c. I ran it for more than half of the day (12-18 hours)
 - d. I ran it for part of the day (6-12 hours)
 - e. I ran it for a few hours (0-6 hours)
- 3. How much did you notice noise from the filter?
 - a. Extremely noisy
 - b. Very noisy
 - c. Somewhat noisy
 - d. Minimal noise
 - e. I didn't hear it at all
- 4. How likely is it that you will buy replacement filters in the future? [Likert scale]
 - a. Very likely
 - b. Somewhat likely
 - c. Not very likely
 - d. Not likely at all
- 5. *[If less than very likely....]* What are some of the reasons why you might not buy replacement air filters (check all that apply)?
 - a. Too costly
 - b. Too inconvenient
 - c. Don't know where to buy them
 - d. Too noisy

- e. Not sure they are effective
- f. Other: _____

6. During the study period did you have a change in your blood pressure medication?

- a. Yes
- b. No
- c. Don't know/refused

7. How concerned are you about the effects of air pollution on your health?

- a. Very concerned
- b. Somewhat concerned
- c. Not very concerned
- d. Not concerned at all

8. Would you be interested in continuing to participant in this study and check your BP twice daily for 3 months?

- a. Yes
- b. No
- c. Don't know/refused

9. If this study continued for 6 months, would you be interested in continuing to participate and check your BP daily?

- a. Yes
- b. No
- c. Don't know/refused

